6.1.4 Handling of Treatment Errors and Discrepancies

In addition to the rules in [Section 6.1.3](#) for handling situations envisaged by the CTP, it is also possible that dosing errors may occur. These could either be errors in the site dispensing an incorrect treatment and/or giving incorrect instructions about how to take the dispensed treatment, or they could be patient administration errors.

Dosing errors (other than through incorrect IRT transactions, as described in [Section 6.1.3](#)) will not change the assignment of any patient to actual maintenance treatment as described above, regardless of the reason for the error, and regardless of the unblinded dose taken or dispensed at the relevant week(s). However, any such errors and their unblinded doses will be identified as part of the analysis.

Blinded identification of potential discrepancies between assigned, dispensed and administered medication numbers will be performed prior to DBL as part of ongoing monitoring for possible IPDs.

6.1.5 Pooling Across Doses

In addition to specific Survodutide dose columns on descriptive summary tables, a combined column across doses (i.e. “All Survodutide”) will also be presented.

Combined Survodutide dose will not be used in any statistical models or descriptive summaries of efficacy.

Combined Survodutide dose will be included on all disposition and demographic/baseline summary tables, and in descriptive summaries of treatment exposure and safety.

Where a short treatment label is required on outputs, “Survo X.X mg” and “All Survo” will be used for the specific dose groups, and the combination across dose groups, respectively.

6.1.6 Definition of On-Treatment

There is no continued study participation for patients who have discontinued treatment early. Consequently off-treatment data capture is expected to be restricted to those data captured during the safety follow-up period specified by the CTP, although there may be occasional unplanned exceptions to this.

Even for patients who completed treatment according to the protocol, data captured during the follow-up period may be relevant for safety.

It is important to be clear whether all available data will be used in a particular summary or analysis, or whether only on-treatment data will be used. The definition of “on-treatment” for this purpose is as described below, and it includes any temporary treatment interruptions which might occur prior to last dose of study treatment. It is assumed that all patients will have a date of last administration of study medication accurately recorded on the End of Treatment eCRF page.

“Off-treatment” refers to data which are captured after baseline but which are not “on-treatment” as defined below.

Safety

An AE start date or other safety assessment date will be considered “on-treatment” if the AE start date or assessment date is between the date of first dose and 28 days after the date of last

dose of study treatment inclusive (the residual effect period (REP) is defined as 28 days in this trial).

The same on-treatment definition will be used for all types of safety data.

Efficacy

All post-baseline efficacy data (including for exploratory biomarkers) will use the same 28-day definition of “on-treatment” as for safety, where on-treatment analyses are specified (as opposed to those efficacy analyses which use all data, both on- and off-treatment).

6.2 IMPORTANT PROTOCOL DEVIATIONS

Handling of IPDs is included in the DV domain specifications and stored within the TMF in EDMS.

IPDs will not lead to exclusion from analysis sets.

6.3 SUBJECT SETS ANALYSED

The following analysis sets will be defined:

Screened Set

The screened set (SS) includes all patients for whom a signed informed consent is available at the time of final DBL. It will be used only for display of patient disposition.

Randomised Set

The randomised set (RS) includes all screened patients who were randomised in the trial, regardless of whether any study drug was taken. It will be used only for display of patient disposition and IPDs.

Treatment assignment will be as randomised (i.e. planned maintenance treatment).

Treated Set

The treated set (TS) is defined as all randomised patients who received at least one dose of study treatment.

The TS will be used for presentation of demographic/baseline data, concomitant medications/diagnoses, treatment exposure, efficacy and safety.

Treatment assignment will be according to both actual maintenance treatment and planned maintenance treatment (i.e. as randomised), depending on the analysis.

It is not expected on the database that the situation in which a patient could be treated without randomisation will exist. Documentation is in place by the Interactive Response Technology (IRT) vendor, which states that, should any patient be given treatment at the site in error

without randomisation, such a patient will be subsequently randomised to a treatment which is not incompatible with the one given in error.

Full Analysis Set

The full analysis set (FAS) was defined in the CTP in the same way as TS. Since the definitions are the same, the TS label will be retained for both efficacy and safety analysis, and the FAS label will not be used.

Per Protocol Set

A per protocol set (PPS) will not be defined in this study.

[REDACTED]

[figure not shown]
[REDACTED]

The table below summarises the analysis sets and their main intended purpose [REDACTED]

[REDACTED]

Table 6.3: 1 Subject sets analysed

| Data type | Analysis set | | | |
|--|--------------|----|----|---|
| | SS | RS | TS | █ |
| Disposition | X | X | | |
| Demographic and baseline characteristics | | | X | |
| Concomitant diseases and medications | | | X | |
| Exposure to study drug | | | X | |
| Primary efficacy endpoint | | | X | |
| Secondary efficacy endpoints | | | X | |
| █ | | | █ | |
| █ | | | █ | |
| Adverse events | | | X | |
| Vital signs | | | X | |
| Laboratory safety data | | | X | |
| 12-lead ECG | | | X | |
| Other safety | | | X | |
| █ | | | | █ |

6.5 POOLING OF CENTRES

No analysis will be performed in which centre is included in the statistical model.

Subgroup analysis will be performed by country and region, but no other pooling of centres will be performed.

6.6 HANDLING OF MISSING DATA AND OUTLIERS

Efficacy

For responder efficacy endpoints using biopsy, MRI-PDFD and [REDACTED] (including the primary endpoint defined in [Section 5.1](#)), patients without data to evaluate the response will be imputed as non-responders (whether the missing data are expected from the CTP schedule or not). For MRI-PDFD this simple non-responder imputation will be used in the main analysis.

[REDACTED]

For continuous efficacy endpoints, missing data will be handled implicitly by the statistical model (mixed model for repeated measures (MMRM)). This model makes the assumption that the data are MAR. Patients who do not have a value at the time point of interest, but who have earlier post-baseline values, still contribute to this analysis. MAR means that a patient who drops out is assumed to have behaved like a similar patient within the same treatment group (where “similar” means both with regard to baseline covariates in the model and to the observed trajectory of post-baseline values prior to drop out).

For continuous endpoints derived from MRI-PDFD and [REDACTED] (only), [REDACTED]

No other imputations will be performed for any efficacy endpoint.

Safety

A completely missing concomitant medication start date will be set to screening date. If only the month and year are available for the AE/concomitant medication start date, the first day of the month will be assumed. If only the year is available, then 1st January of that year will be assumed. In the case of AE start dates (only), if the stated imputation would make the AE become pre-treatment when this was not known from the incomplete date, it will be assumed instead that the AE started on the first day of treatment.

If only the month and year are available for date of last administration of study medication, the last day of the month will be assumed.

If only the month and year are available for the date of first administration of study medication, the date of randomisation will be used if they are in the same month. If randomisation was in the month prior to first drug administration, the first day of the month of first administration will be assumed.

6.7 BASELINE, TIME WINDOWS AND CALCULATED VISITS

Definition of baseline

In general, baseline is defined as the last non-missing measurement on or prior to the first administration of study medication. In the case that the first dose of study medication is delayed beyond the date of randomisation, a post-randomisation value can be used as a baseline value provided that it meets the stated requirement.

Where clock times are available (expected to include laboratory safety data, 12-lead ECG, plasma Survodutide concentrations and biomarkers) they will be used in addition to dates to define baseline, since it is also expected that the time of first study drug administration will be accurately recorded on the eCRF for all patients.

Unscheduled and repeat assessments are eligible for use as baseline values provided that they meet the above criterion.

For 12-lead ECG, if a screening value needs to be used for baseline, it will be the average of all available triplicate screening ECG measurements (see [Section 5.4.1](#) for derivation details).

For vital signs, the baseline definition will make the additional requirement that the data records are pre-dose. In practice, this will also be done using the clock times as well as the date. A single pre-dose measurement is expected to be captured at the baseline visit (Visit 2), which will therefore be used as baseline. In any situation in which only a post-dose measurement is available at Visit 2 and no pre-dose measurements, Visit 2 will not be used as baseline; the screening visit (Visit 1) will be used as baseline instead.

For baseline NAS and fibrosis scores, the following specific considerations will be applied:

- Either a biopsy performed during the screening period or a historical biopsy (within 6 months) will be used to provide baseline data, without any further distinction made for analysis purposes between these two situations (both referred to subsequently as “screening biopsy”).
- The baseline value will be derived from central pathology readings of screening biopsy slides. For sites in all countries except China, central pathology screening readings will always be physical readings. For sites in China, central pathology screening readings may be digital readings, the handling of which is described below.
- All adequate central pathology readings which meet the baseline definition will be used, including any (expected to be occasional) readings performed by the back-up

reader instead of the primary reader. The meaning of “adequate” is given in [Section 5.1](#).

- The first screening central pathology reading (i.e. as used to assess eligibility) will be used for baseline in all cases where a re-reading of the screening biopsy was subsequently done, unless otherwise specified for any analysis. For sites in China (only), the first screening central pathology reading is a digital reading and this will be used.

MRI-PDF and [REDACTED] procedures are only scheduled to be performed at screening, and not also at the randomisation visit. Therefore, the baseline value is the screening value in these cases.

Visit windows

All summaries and analysis which are presented by week will use a visit window to classify the data record. This approach allows appropriate classification of visits which may have occurred significantly earlier or later than the protocol assessment schedule, as well as the use of data captured at visits which have no fixed timing (notably the EOT visit). Relative day will be defined for this purpose as $(date\ of\ assessment - date\ of\ first\ administration\ of\ study\ medication) + 1$.

Nominal database visit labels will not be used in any summary or analysis by time point, unless otherwise stated.

Prior to applying the rules for handling multiple values in visit windows specified below, it will first be determined whether the data record is on-treatment, as defined in [Section 6.1.6](#), for all summaries or analysis which require this approach.

Unscheduled and repeat assessments (where relevant/available) are eligible for inclusion in visit windows.

For all variables except 12-lead ECG, if a patient has more than one non-missing value within the same visit window, the value closest to the target day will be selected. If two non-missing values are the same distance from the target day, the earlier of the two values will be selected.

For 12-lead ECG (only), scheduled visits take precedence over unscheduled visits. Once this rule has been applied, the measurement closest to the target day will be used. If there are two observations which have the same difference in days to the planned day (but are not on the same day), the later of the two values will be selected.

Derivation of last, minimum and maximum values where relevant in safety analyses will consider all available values, regardless of whether they were selected in the visit window.

The derivation of the maximum value of an ECG interval (or worst case of the morphological assessment, if applicable) will consider all on-treatment values (whether or not selected in any time window; see [Section 6.1.6](#) for definition of on-treatment).

Four different situations are envisaged, which are described in the following tables:

- Visit windows for variables scheduled to be assessed at all or most clinic visits
- Visit windows for biomarker variables
- Visit windows for variables with an intermediate clinic visit schedule
- Visit windows for variables with a sparse clinic visit schedule

Table 6.7: 1 Visit windows for variables scheduled to be assessed at all or most visits

| Period | Time Point | Target Day | Visit Window |
|-----------------|-------------------|-------------------|---------------------|
| Dose escalation | Week 1 | 8 | 2-11 |
| | Week 2 | 15 | 12-18 |
| | Week 3 | 22 | 19-25 |
| | Week 4 | 29 | 26-35 |
| | Week 6 | 43 | 36-49 |
| | Week 8 | 57 | 50-63 |
| | Week 10 | 71 | 64-77 |
| | Week 12 | 85 | 78-98 |
| | Week 16 | 113 | 99-126 |
| | Week 20 | 141 | 127-154 |
| Maintenance | Week 24 | 169 | 155-182 |
| | Week 28 | 197 | 183-210 |
| | Week 32 | 225 | 211-238 |
| | Week 36 | 253 | 239-266 |
| | Week 40 | 281 | 267-294 |
| | Week 44 | 309 | 295-322 |
| | Week 48 | 337 | ≥ 323 |

The relevant variables are expected to include vital signs, routine laboratory safety variables (all expected to be non-fasting), 12-lead ECG and the mental health questionnaire (C-SSRS).

In particular, the Week 2 and Week 4 visit windows from this table will still be used for laboratory safety variables and 12-lead ECG, even though these are not also scheduled at Week 1 and Week 3.

Table 6.7: 3 Visit windows for variables with an intermediate visit schedule.

| Period | Time Point | Target Day | Visit Window |
|-----------------|-------------------|-------------------|---------------------|
| Dose escalation | Week 8 | 57 | 2-84 |
| | Week 16 | 113 | 85-154 |
| Maintenance | Week 28 | 197 | 155-266 |
| | Week 48 | 337 | ≥ 267 |

The relevant variables are expected to be body weight / BMI derived from this, waist circumference and hip circumference.

Table 6.7: 4 Visit windows for variables with a sparse visit schedule.

| Period | Time Point | Target Day | Visit Window |
|-------------|------------|------------|--------------|
| Maintenance | Week 28 | 197 | 2-266 |
| | Week 48 | 337 | ≥ 267 |

The relevant variables are expected to be MRI-PDFP and the [REDACTED].

The use of such a wide visit window for MRI-PDFP at Week 28 means that it will include and display/analyse as “Week 28” any MRI assessments which were done unexpectedly early.

Post-baseline biopsy

Patients are scheduled to provide data from a single post-baseline biopsy at Week 48, which may be earlier (expected 40 weeks onwards) for patients who discontinued early, but nevertheless remained on treatment for long enough to justify performing the biopsy. Two different ways of handling this in analysis are planned, and these are expected to be identical if the protocol requirements are followed exactly:

- All post-baseline biopsy data are used, regardless of how early the biopsy was done (this is equivalent to specifying a single visit window for “Week 48” as ≥ 2 days)
- Only post-baseline biopsy data are used which are after 40 weeks (this is equivalent to specifying a single visit window for “Week 48” as ≥ 280 days)

Vital signs

For vital signs, the following windowing rules will be applied within each visit to determine pre-dose and 10 minutes post-dose from recorded clock times:

- If the vital signs measurement time is prior to or equal to the time of study drug administration, then it is considered eligible for pre-dose, without restriction on how long before study drug administration the measurement was done (provided it was still done on the same visit date). If this selects more than one value as “pre-dose”, the latest will be used.
- If the vital signs measurement time is after the time of study drug administration, then it is considered eligible for post-dose, without restriction on how long after study drug administration the measurement was done (provided it was still done on the same visit date). If this selects more than one value as “post-dose”, the value closest in time to the target 10 minute post-dose time point will be used.

The situation in which vital signs measurement time is exactly equal to the time of study drug administration is not clinically plausible, and a rule for handling it is included above only for completeness, in case this cannot be resolved for any patients and this situation remains on the database at final DBL.

Any vital signs record for which no time of study drug administration exists (expected to include measurements recorded during the 28 day REP and scheduled Week 48 measurements) will be considered “pre-dose” according to the above rules. Only pre-dose measurements will be used for efficacy purposes (blood pressure further endpoints).

7. PLANNED ANALYSIS

Descriptive statistics for continuous variables will generally include N (number of patients with non-missing values), arithmetic mean, standard deviation (SD), minimum, Q1 (lower quartile), median, Q3 (upper quartile) and maximum. In general, means, medians, other quartiles and SDs will be presented to one more decimal place than the raw data. Minimums and maximums will be presented to the same number of decimal places as the raw data.

Tabulations of frequencies for categorical data will include all possible non-missing categories unless otherwise specified, and will display the number of patients in a category as well as the percentage (%) relative to the respective treatment group. Percentages will be rounded to one decimal place. A missing category will be displayed only if there are actually missing values. Percentages will be based on all patients in the respective patient set whether they have non-missing values or not.

Disposition

The disposition of patients will be displayed. This table will present the number of patients enrolled, randomised and treated. The number treated will be further presented separating the dose escalation and maintenance periods. Planned maintenance treatment (see [Section 6.1.2](#)) will be used for this table.

The number of patients who completed or who prematurely discontinued study treatment will be summarised, along with the categorization of the primary reason for treatment discontinuation. The number of patients and reasons for prematurely discontinuing treatment will also be displayed separately for the dose escalation and maintenance periods.

The number of patients who completed or who prematurely withdrew from the study will be summarised, along with the categorization of the primary reason for study withdrawal. It should be noted that in this study, a patient is considered to have completed the study if all scheduled safety follow-up procedures have been performed for that patient, including for patients who discontinued treatment early. In other words, a patient may complete this study without completing treatment.

Where shown on the disposition table, the percentages will be of the number of patients treated in each treatment group.

Kaplan-Meier estimates will be presented graphically by planned maintenance treatment group for time to early treatment discontinuation (defined as *treatment discontinuation date*

– *treatment start date + 1*). In this analysis, patients who did not discontinue treatment early will be censored using the date on which they completed treatment.

The frequency of patients in each of the different analysis sets ([Section 6.3](#)) will also be tabulated by planned maintenance treatment.

A shift table will be produced to display differences between planned maintenance treatment and actual maintenance treatment.

A shift table will also be produced to display differences between the first and last doses of maintenance treatment (for patients who reached the maintenance period). This shift table will be produced separately using both dispensed and administered dosing.

IPDs will be summarised and listed for the randomised set using planned maintenance treatment.

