#### Residual Effect Period

The Residual Effect Period (REP) of BI 456906 is 28 days. This is the period after the last dose with measurable drug levels and/or pharmacodynamic effects still likely to be present.

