The NOAEL for BI 456906 in cynomolgus monkeys is only limited by the effect on body weight loss which reflects the pharmacology of the compound. Obviously, especially female monkeys with a profound lower initial body weight than male monkeys have to be considered oversensitive.

The lowest dose of 2.4 mg/ week in this trial is predicted to achieve sub-therapeutic PD response comparable to placebo in patients with NASH and fibrosis, however, still providing weight loss and improvement in the metabolic status.

The results from the 1404-0003 indicate that the most common GI adverse events such as nausea and vomiting occur at the beginning of the drug exposure and can be mitigated by a careful dose escalation. The tolerability of GLP-1 receptor agonists is known to improve over time, so is assumed that even higher doses of BI 456906 will be tolerated [[R20-0479](#)]. In addition, close monitoring is implemented in this trial to assure patients' safety.

Overall, the three selected maintenance doses are anticipated to support robust dose-exposure-response analyses for multiple safety and efficacy measures to serve as a basis for selection of the suitable dose regimen for the phase III trial.

Selected doses cover a safe starting dose of 0.3 mg/ week with different dose escalation schemes up to the target maintenance dose. The first 10 weeks of the dose escalation period will be identical for all three active treatment groups. The duration of the dose escalation up to the target maintenance dose differs among the active treatment groups from 14 to 22 weeks.

Dose adjustment will be allowed in all groups during the dose escalation period after Visit 14 as well as any time during the maintenance period based on the occurrence of AEs. If a patient does not tolerate a dose due to AEs in the previous two weeks and wishes to reduce the dose, then the dose should be decreased to the next lower tolerated target maintenance dose. The assignment of the lower dose will occur in a blinded fashion via IRT.

Examples:

- If a patient who does not tolerate a dose of 2.4 mg over two weeks during the dose escalation period and wishes to reduce the dose will be changed to placebo;
- If a patient who does not tolerate a dose of 3.6 mg over two weeks during the dose escalation period and wishes to reduce the dose will be changed to 2.4 mg;

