5.4.3 Treatment exposure and compliance

Treatment exposure is defined as the number of days from the first dose of study treatment to the last dose of study treatment inclusive. Any intermediate gaps in treatment in which the patient did not take medication will not be considered. It is assumed that an End of Treatment eCRF page will be available and complete for all treated patients at DBL, and that no special rules are needed to handle any missing information here.

Treatment exposure duration will be categorized as follows:

<4 weeks; 4-<8 weeks; 8-<12 weeks; 12-<16 weeks; 16-<20 weeks; 20-<24 weeks, 24-<28 weeks; 28-<32 weeks; 32-<36 weeks; 36-<40 weeks; 40-<44 weeks; 44-<48 weeks; \geq 48 weeks.

Study duration (regardless of whether on-treatment) will also use the same category definitions, although significant off-treatment follow-up after stopping treatment is not expected in this trial.

No treatment compliance calculations will be performed for analysis purposes based on return of unused and empty syringes. Any discrepancies between medication assigned, medication dispensed and medication administered will be assessed through the process for determining IPDs.

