6.1.3 Actual Maintenance Treatment Group

According to the rules for escalating and adjusting the Survodutide dose given in the CTP, it is envisaged that some patients may not receive the planned maintenance treatment according to the randomised treatment group, whilst nevertheless remaining on treatment.

Actual maintenance treatment group will be defined for analysis as follows:

- If the patient started the maintenance period, then actual maintenance treatment group will be defined in all circumstances to be the dose at the start of the maintenance period (which is expected to be one of the Survodutide maintenance doses), regardless of whether previous dose escalation was performed in the expected way according to the protocol. This includes each of the following situations:
 - Any patient who successfully reached their planned maintenance dose at the end of the dose escalation period
 - Any patient who did not reach their planned maintenance dose at the end of the dose escalation period, and who only reached a lower maintenance dose
 - Any patient for whom the start and end maintenance dose are not the same, regardless of whether the patient started the maintenance period on their planned maintenance dose, and regardless of whether the permanent dose reduction was planned according to the protocol, or whether it was unplanned (e.g. where the wrong tolerability information was given to the IRT and the dose was not re-escalated back to correct the error).
- If the patient discontinued treatment during the dose escalation period, actual maintenance treatment group will be defined as the next planned maintenance dose up from the dose at discontinuation. The same rule will be applied irrespective of the reason for discontinuing treatment during the dose escalation period, and will be applied irrespective of whether the dose prior to the dose at discontinuation was as anticipated from the protocol dose escalation strategy.

Table 6.1.3: 1 Definition of actual maintenance treatment group for patients randomised to active Survodutide maintenance treatment who discontinued treatment during the dose escalation period

| Dose at discontinuation | Actual maintenance treatment group |
|---|------------------------------------|
| Dose = 0 mg | Placebo |
| $0.3 \text{ mg} \leq \text{Dose} \leq 2.4 \text{ mg}$ | 2.4 mg |
| $2.4 \text{ mg} < \text{Dose} \leq 4.8 \text{ mg}$ | 4.8 mg |
| Dose > 4.8 mg | 6.0 mg |

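### A survodutide patient moved to placebo for intolerance has no event in the discontinuation outputs, and the exposure tables do not separate survodutide time from placebo time

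*SAP*

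**What the plan says.** **The switch.** Protocol 4.1.2 allows dose reduction for intolerance in escalation (at Visits 16, 18, 20, 22 and 24) and throughout maintenance. The general rule is that "the dose should be decreased to the next lower tolerated target maintenance dose". The escalation example for 2.4 mg is a patient who "wishes to reduce the dose will be changed to placebo". The change is made blind through the IRT.

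**Discontinuation.** SAP 7 (Disposition) counts completion and early discontinuation of study treatment by planned group. "Kaplan-Meier estimates will be presented graphically by planned maintenance treatment group for time to early treatment discontinuation", and "patients who did not discontinue treatment early will be censored using the date on which they completed treatment". A change to placebo is not listed as an event.

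**Exposure.** SAP 5.4.3: "Treatment exposure is defined as the number of days from the first dose of study treatment to the last dose of study treatment inclusive". Placebo doses given to a patient randomised to survodutide are not separated. SAP 7.7 shows exposure by both planned and actual group, and SAP 7.8 does the same for safety.

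**Actual group.** Under SAP 6.1.3, patients switched to placebo during escalation are assigned to placebo. Patients who started maintenance keep their starting maintenance dose, and this covers "Any patient for whom the start and end maintenance dose are not the same".

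**The concern.** For a patient randomised to survodutide, a change to placebo ends survodutide because of intolerance. The outputs that a reader would consult on tolerability by dose do not register it. A patient who finishes on placebo is a completer. One who later stops the placebo injections has an event, but at the later date.

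The effect is uneven across arms. Stepping down from 4.8 or 6.0 mg normally leaves the patient on survodutide, whereas stepping down from 2.4 mg does not. It also changes at Visit 14. Before then, intolerance stops all trial medication and counts as a discontinuation. Afterwards, a 2.4 mg patient with the same problem can go to placebo and not count.

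This matters because SAP 7.4.1 says that tolerability and safety will be weighed alongside efficacy in choosing the Phase 3 dose. A discontinuation curve that omits these patients makes 2.4 mg look better tolerated than it was.

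**Working it through.** The documents state no switch rate, discontinuation rate or exposure total, so there is no figure to reproduce. The check traces the rules and then does the day arithmetic.

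**Inputs**
- 60 patients per arm (Protocol synopsis and 7.5).
- Weekly doses from Day 1, the last one week before Visit 32 (Protocol 6.2.2). That is Week 47, day 47 × 7 + 1 = 330.
- Escalation adjustments at Visits 16 to 24, which are Weeks 14 to 22 (Protocol 4.1.2 and Flow Chart).
- The 2.4 mg arm first receives 2.4 mg at Visit 16 (Protocol Table 4.1.4: 1). The protocol's example, 2.4 mg not tolerated for two weeks, can therefore first lead to a switch at Visit 18 (Week 16). A Visit 16 switch would apply the general step-down rule to the 2.1 mg doses and is the outer bound.

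**Step 1: where a switched patient appears**

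| Output | Switch in escalation | Switch in maintenance |
|---|---|---|
| Disposition and Kaplan-Meier (planned group) | No event at switch | No event at switch |
| Exposure and safety, planned group | Placebo weeks count as the randomised dose | Placebo weeks count as the randomised dose |
| Exposure and safety, actual group | All time counts as placebo, including survodutide weeks | Placebo weeks count as 2.4 mg |

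**Step 2: discontinuation.** If k switched patients in an arm of 60 complete on placebo, the proportion stopping survodutide is understated by k/60: 1/60 = 1.7, 3/60 = 5.0 and 6/60 = 10.0 percentage points. The values of k are illustrations.

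**Step 3: exposure per switched patient.** For a switch at Week w, the last survodutide dose falls on day 7(w − 1) + 1. Placebo days counted as exposure are 330 minus that day.

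| Switch | Last survodutide day | Placebo days | Share of 330 |
|---|---|---|---|
| Week 14 (Visit 16) | 92 | 238 | 72% |
| Week 16 (Visit 18) | 106 | 224 | 68% |
| Week 22 (Visit 24) | 148 | 182 | 55% |
| Week 28 | 190 | 140 | 42% |
| Week 40 | 274 | 56 | 17% |

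The first three rows are escalation switches. Their placebo days count as the randomised dose only in the planned-group tables. In the actual-group tables the 92 to 148 days up to the last survodutide dose count as placebo, with the AEs that occurred in them. The last two rows are maintenance switches, and their placebo days count as 2.4 mg in both sets for a patient who began maintenance on 2.4 mg.

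**Step 4: exposure for the 2.4 mg arm, planned group.** Suppose 6 of 60 switch and every patient takes the full course. At Week 16 the placebo time is 6 × 224 = 1,344 days, and exposure is inflated by 1,344/(60 × 330 − 1,344) = 1,344/18,456 = 7.3%. At Week 28 it is 6 × 140 = 840 days, and 840/18,960 = 4.4%.

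**The case against.** The best defence is that the SAP reports discontinuation of blinded study treatment and counts it correctly as defined. The protocol treats the change as a dose adjustment, and the patient continues injections and visits. That stands. What is understated is the stopping of survodutide, which is a different quantity.

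The shift tables in SAP 7 (planned versus actual dose, first versus last maintenance dose) will show how many patients moved. That also stands, but they give no timing and correct no curve, rate or exposure total.

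Four stronger readings are tempting, and the documents do not support them:

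- A reader might infer that placebo weeks always count as 2.4 mg exposure. SAP 6.1.3 sends escalation switches to placebo in the actual-group tables, where the error runs the other way.
- A reader might infer that the exposure-adjusted rate of the AE behind the switch is diluted by placebo time. Under SAP 7.8.1, time at risk for an AE term ends at its first event. Only terms the patient has not yet had can be diluted.
- A reader might infer from "The Residual Effect Period (REP) of BI 456906 is 28 days" that the 28-day window cannot run from a placebo injection. Protocol 7.2.1 and SAP 6.1.6 apply that window to every arm, placebo included. Shortening it in the main tables would drop observed AEs from as-randomised summaries for active-arm switchers only.
- A reader might take a particular switch rate as given. None is, and every allocation variation in Protocol 7.5 keeps placebo at 60.

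Two steps are inferences. That the switch is permanent rests on the absence of any re-escalation rule after a tolerability reduction. That it can occur in maintenance follows from the general step-down rule, since the protocol's placebo example concerns escalation only.

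**Conclusion.** The point holds in a limited form. In the planned-group disposition table and Kaplan-Meier curve, stopping survodutide for intolerance by a switch to placebo is missed or dated late, mainly in the 2.4 mg arm. The size is 1.7 percentage points per switched patient who completes on placebo. The total cannot be stated because the number of switches is unknown.

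The exposure tables mix survodutide and placebo time, in a direction that depends on the table and on when the switch occurred. These are gaps in the tolerability description. Study-treatment discontinuation as the SAP defines it is not miscounted, and the primary MCPMod analysis uses neither discontinuation nor exposure.

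**What to change.** From the unblinded dosing data, derive a date of last survodutide dose for every patient randomised to survodutide. Beside the existing displays, add:

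1. In SAP 7, a Kaplan-Meier curve and a disposition row by planned treatment in which a switch to placebo is an event at that date.
2. In SAP 7.7 and 7.8.1, exposure and key AE summaries by planned treatment limited to survodutide time, with the 28 days after it included for AEs (SAP 7.7 already leaves them out of patient-years).

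Keep the current study-treatment and on-treatment definitions for the main tables. Attributing a triggering AE to each switch is not proposed: the documents do not show that the necessary data are recorded, and investigators are blinded to the change.

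The cost is one derived date and a few extra outputs from data already collected; SAP 6.1.3 already plans an unblinded dosing review after database lock. If switches occur, the 2.4 mg discontinuation rate will look somewhat less favourable. No clinical rule changes.
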